12 WITHDRAWAL OF SUBJECTS

12.1 Anticipated Circumstances Under Which Subjects Will be Withdrawn From the Research Without Their Consent

Participants will be withdrawn from the study if they do not follow the study schedule or requirements. Participants are expected to reach 80% EMA compliance daily (>4 of 5 prompts). If a participant fails to reach 80% compliance for 3 consecutive days, that participant will be warned and retrained. If the participant continues to be noncompliant for 3 additional days, they will be withdrawn from the study. Failure to respond to any study prompts (0% compliance) for three consecutive days will result in withdrawal.

12.2 Procedures That Will be Followed When Subjects Withdraw From the Research, Including Partial Withdrawal From Procedures With Continued Data Collection

The participants will only be paid for the completed study sessions and then will be dismissed from the study.

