Cigarette tracking via EMA: For the field study, the key outcome is the total number of cigarettes smoked. Participants will be asked to complete REDCap questionnaires on their personal phone (iOS or Android). Participants can use the MyCap application to respond to questionnaires. Additionally, REDCap can interface with Twilio, a secure text-messaging platform, to send study related messages and surveys via SMS (text messaging). Proposed EMA methods are based on established best practices. Participants will complete 5 questionnaires every day. These questionnaires will occur at the same time each day: 11am, 1:30pm, 4pm, 6:30pm, and 9pm. These daily reports will be used to assess cigarette and e-cigarette consumption, and 10 items relating to subjective ratings of nicotine withdrawal (e.g., craving, irritability) and mood (e.g., calm/relax, happy). At 11am only, participants will complete selected items from the Hedonic Attribute Profile and Product Evaluation Scale. At 9pm only, participants will be asked to rate the taste, satisfaction,

Roswell Park Protocol Number: I 757820

enjoyment, and craving relief from the cigarettes they smoked that day. Participants will also be asked to take a CO measurement at this time. At the 1:30 and 6:30 prompts, participants will be asked about situational factors related to use (Location, smoking permitted, with others, activity, craving) and complete the Duke Sensory Evaluation scale. Participants also will be asked to take a picture of their research cigarette pack to ensure compliance. Surveys will be open for 1 hour after the scheduled time for completion. Appendix C demonstrates the EMA schedule and the questions asked at each daily report and pseudo-random prompt. Participants can earn up to \$10 for each day of EMA compliance, with compliance being defined as responding to ≥ 4 of 5 daily prompts (up to 14 days, totaling \$140). Studies that used similar methods had $>90\%$ compliance. [189, 190].

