Appendix D: Experimenter Guide

1. Welcome and Introductions:

2. Introduction:

- I would appreciate if you can minimize distractions until our videoconference is done. If something important requires your attention, please let me know and we can take a brief pause.
- First, I'll ask you to complete an online questionnaire. Here, we are looking for some information about you and your tobacco use.
- We will then move onto training you on study procedures.
- There is no right or wrong answer here. You are the expert and we are really interested in your honest responses to questions and to the tasks during the laboratory session.
- Do you have any questions?

*Answer any questions.

3. Baseline Questionnaires

- "We will now begin the baseline questionnaires."
 - Baseline measures and covariates will assess:
 - Demographics (age, sex, race/ethnicity, education, income)
 - Tobacco use behaviors (consumption, brand, menthol preference, quit history)
 - Cognitive and affective measures
 - A series of previously used items will assess knowledge and perceptions of filter vents.^{113,117}
 - Nicotine dependence will be assessed using:
 - Fagerström Test for Nicotine Dependence (FTND;¹¹⁸)
 - Behavioral aspects of cigarette dependence will be assessed using:
 - The Glover-Nilsson scale^{120,121}
 - Questionnaires on vent messages
 - Questionnaires on message perceptions

We will now train you and provide you with supplies for the field study

Field Study Description

For the field study, you are going to use your mobile device to record your cigarette and other tobacco use and answer questions about how you're feeling and the situations in which you use your products. You will be prompted 5 times each day via text message to answer questionnaires. Three of these prompts will be at the same time every day: 11am, 4pm, and 9pm. Two of these prompts will be at a random time each day, one between 11am – 4pm and one between 4pm – 9pm. To receive bonus payment for the field study, you will need to respond to

Roswell Park Protocol Number: I 757820

all 5 prompts. If you fail to respond to prompts for 3 consecutive days, we will send you a warning. If compliance to procedures does not improve, you will be discontinued from the study.

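### Section 12.1 equates 80% daily EMA compliance with more than 4 of 5 prompts, which is 100%, and the Appendix D script states different payment and non-response rules

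*Combined protocol and SAP*

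**What the plan says.** Section 11.4 sets the prompt schedule: "Participants will complete 5 questionnaires every day". It pays up to $10 for each compliant day (14 days, $140), with "compliance being defined as responding to ≥ 4 of 5 daily prompts".

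Section 12.1 sets the rules for withdrawal without consent:

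- Expectation: "Participants are expected to reach 80% EMA compliance daily (>4 of 5 prompts".
- Warning step: "If a participant fails to reach 80% compliance for 3 consecutive days, that participant will be warned and retrained".
- Withdrawal step: "If the participant continues to be noncompliant for 3 additional days, they will be withdrawn from the study".
- Separate rule for silence: "Failure to respond to any study prompts (0% compliance) for three consecutive days will result in withdrawal".

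The script in Appendix D (Experimenter Guide) tells participants: "To receive bonus payment for the field study, you will need to respond to". After a page break, that sentence ends by requiring all five prompts. The script continues: "If you fail to respond to prompts for 3 consecutive days, we will send you a warning". It adds that participants will be discontinued if compliance does not improve. It gives neither the 80% level nor the number of further days in 12.1.

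No other section reconciles these statements.

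**The concern.** The sentence that sets the expected standard gives two thresholds, a percentage and a prompt count, and they disagree. The case that separates them is the day with exactly four answered prompts, which is a common one: at an assumed 90% response per prompt it makes up about a third of days.

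The standard feeds a rule that removes randomised participants without their consent. Under section 12.2 a withdrawn participant is paid only for completed sessions and is dismissed. EMA also supplies cigarette consumption, which 11.4 calls the key outcome of the field study. Three sites could apply different cut-offs from the same text. Participants could also be told one payment rule and paid under another.

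**Working it through.** **1. The plan's own figure.** With five prompts, 4/5 = 80%. The only whole number above 4 and not above 5 is 5, and 5/5 = 100%. The 80% is reproduced by at least 4 of 5 and not by more than 4 of 5.

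**2. A day with exactly four answered prompts, statement by statement.**

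| Statement | Status of a 4-of-5 day |
|---|---|
| 12.1, percentage (80%) | meets it |
| 12.1, prompt count (>4 of 5) | fails it |
| 11.4, payment (≥4 of 5) | compliant, paid |
| Appendix D, payment (all 5) | unpaid |

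**3. Three consecutive days with no response at all.** Section 12.1: withdrawal, with no warning step stated in that rule. Appendix D: a warning, then discontinuation if there is no improvement.

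**4. How much the threshold could matter.** This part is illustrative. Assume that each prompt is answered with probability p, independently, and that p stays constant over 14 days.

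- Compliant day under 5 of 5: p^5. At p = 0.90 this is 0.5905.
- Compliant day under at least 4 of 5: p^5 + 5p^4(1−p). At p = 0.90 this is 0.5905 + 0.3281 = 0.9185 (after rounding).
- Noncompliant day, q: 0.4095 against 0.0815.

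A day-by-day recursion over 14 days then follows the 12.1 sequence: three consecutive noncompliant days bring a warning, and three additional noncompliant days bring withdrawal. The text allows three readings of the additional days:

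- (a) the next three days, so six in a row;
- (b) any later run of three consecutive days;
- (c) any three later days.

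The separate zero-response rule adds almost nothing under this model. At p = 0.90 a fully silent day has probability 0.1^5 = 0.00001.

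| p | Threshold | P(compliant day) | P(warned) | Withdrawn (a) | Withdrawn (b) | Withdrawn (c) |
|---|---|---|---|---|---|---|
| 0.95 | 5 of 5 | 0.774 | 10.7% | 0.1% | 0.4% | 1.8% |
| 0.95 | ≥4 of 5 | 0.977 | 0.01% | <0.01% | <0.01% | <0.01% |
| 0.90 | 5 of 5 | 0.590 | 44.8% | 2.7% | 8.8% | 21.6% |
| 0.90 | ≥4 of 5 | 0.919 | 0.6% | <0.01% | <0.01% | about 0.01% |
| 0.85 | 5 of 5 | 0.444 | 75.8% | 13.4% | 33.2% | 54.1% |
| 0.85 | ≥4 of 5 | 0.835 | 4.5% | 0.02% | 0.07% | 0.4% |

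The bound of under 0.5% for at least 4 of 5 holds at these three rates. At p = 0.80, reading (c) gives 3.6%.

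**5. Payment.** If payment is made day by day, expected EMA pay at p = 0.90 is 140 × 0.9185 = $128.6 under 11.4 and 140 × 0.5905 = $82.7 under the script.

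**The case against.** The strongest reply is that the sentences in 12.1 that lead to action turn on the percentage. The warning follows a failure to reach 80%, and more than 4 of 5 appears only in parentheses after the expectation. Someone who answers four prompts reaches 80% and does not trigger the warning. Section 11.4 also uses at least 4 of 5, so the odd item may be a single mistyped or misread symbol. This stands in large part. A reader might infer that 12.1 as written would withdraw people who meet 80%, but that gives the parenthesis priority over the trigger. What remains is a decision rule whose two halves disagree. The misread-symbol explanation is possible but unproven, since 11.4 kept its ≥ sign in the same text.

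The removal rates are also open to challenge, and rightly. Section 11.4 cites compliance above 90% in similar studies but does not say that this is a per-prompt rate. The model gives no credit for the Day 3 check-in (11.3) or for retraining after a warning. Both should lower the rates, and reading (a) gives far smaller figures than reading (c).

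The script can be defended as well. Its line on three days may be a loose paraphrase of the warning step for falling below 80%, in which case it is incomplete rather than contradictory. That is a fair reading for partial responders. For a fully silent participant the two texts still give different outcomes. The requirement of all five prompts governs payment only, so it cannot withdraw anyone and should not be read as a second withdrawal threshold.

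**Conclusion.** The inconsistency is certain and needs no assumption: 80% and more than 4 of 5 cannot both be the daily standard. The payment conflict between 11.4 and Appendix D is equally plain. The conflict over three days without response is real for a fully silent participant and ambiguous otherwise.

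The size of the effect is not fixed by the documents. Across the three readings of the additional days, a literal 5-of-5 rule would withdraw about 0.1-2% at p = 0.95, 3-22% at 0.90 and 13-54% at 0.85. Under at least 4 of 5 the figure is under 0.5% at each of these rates. All of this rests on independent prompts with a constant response rate.

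A reader might infer that such withdrawals would add to the 20% drop-out in section 22.1. The documents do not support that: 22.1 states a total drop-out rate (300 × 0.8 = 240) and does not exclude withdrawals made under the protocol's own rules. Nor does the power statement use the compliance threshold. This is a low-cost consistency correction to a withdrawal and payment rule, not a threat to the stated power.

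**What to change.** - Reconcile 11.4, 12.1 and the Appendix D script to one daily compliance figure, with the percentage and the prompt count in agreement. Which figure applies is for the investigators to decide.
- State one consequence for three consecutive days of non-response, and have 12.1 and the script give it alike. If total silence and falling below the daily standard are meant to lead to different actions, the script should say so.
- State in 12.1 whether the 3 additional days must follow directly, must be consecutive, or may be any three, and carry the daily standard and this step into the script.
- Use the same text at all three sites.

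The cost is about one symbol or figure in 12.1, a clarifying phrase there, and two or so sentences in the script. No recalculation of sample size is needed.

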11.3 Study Procedures

The proposed study is a between-subjects design in which participants will be randomized to 1 of 4 conditions for 2 weeks.

- No Message (e.g., unaltered cigarette pack).
- Neutral Message: “Nothing about this product’s color or name means that it will protect a smoker from the health risks of smoking.”
- Compensation Message: “This product has a ventilated filter. Filter vents increase how deeply a smoker inhales without them knowing, which can increase the health risks of smoking.”
- Blocking Message: “This product has a ventilated filter. Be sure not to block the vent holes with your fingers or lips, which can increase the health risks of smoking.

Data will be collected in three remote video sessions and via EMA conducted over 2 weeks. Each study session is expected to take 0.5 hours. For each condition, active data collection is expected to take no more than 15 minutes. Study materials (cigarettes, CO monitor, containers for cigarette filter collection, scales) will be mailed to, delivered, or picked up by participants. Session 1 will involve confirmation of receipt of study materials, questionnaires, and training on procedures. Then, participants will track their product use via EMA app (REDCap) for 2 weeks, with two remote sessions via videoconference for additional questionnaires.

Informed Consent. An initial videoconferencing session will be used for informed consent. Consent will be obtained through the REDCap (Research Electronic Data Capture) system used for data collection. REDCap is a secure web-based application that supports data capture and management for research studies. The Investigator and Research Associate will design the study specific consent and upload the most recent CRS versions to the REDCap system. A secure link will be sent to each participant prior to the start time of the study. Research staff will guide the participant form, provide time to read the consent, and answer any questions. Participants and staff will be able to electronically sign, data, and submit the consent in real-time. Once the consent is submitted, it is automatically saved on RPCI protected servers. Access to this folder is restricted to authorized users. Standard protocols for data encryption (via Credant) when using laptops and USB drives will be followed.

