In the event of REDCap being inaccessible for a study visit, .pdf files or paper copies of the consent will be provided to the participants and the participants will be able to sign and return or submit a photo of the signed copy.

The participant will then be randomized to 1 of 4 message conditions (No message, Neutral message, Compensation message, Blocking message) and arrangements will be made to mail, deliver, or have participants pick up study materials (study cigarettes with pack messages, CO

Roswell Park Protocol Number: I 757820

monitor, scales, butt collection materials, shipping materials, etc.). Participants will be provided with two weeks of materials.

Session 1. Session 1 will occur upon receipt of study materials by the participant. Participants will complete a baseline intake questionnaire including smoking and tobacco use history, nicotine dependence scales, SCQ, TRIRISK, delay discounting, respiratory symptoms, and knowledge, attitudes, and beliefs about filter vents. In addition, participants complete questionnaires on message perceptions (response to messaging, health risk, purchase intention) for all pack messages. Questionnaires also will be used to get baseline assessments of the user's usual brand of cigarettes (Duke Sensory Scale, Product Evaluation Scale, Hedonic Attribute Scale). Participants will be instructed to record each smoking event using the EMA app provided (described in more detail below) and to retain all spent cigarette butts and unused product. Participants will be informed that they are free to use other tobacco products (though they will not be provided as part of the study), and that these should be recorded using EMA. Participants will be provided for cigarettes for a total of two weeks, with the amount determined by normal self-reported weekly consumption rounded to nearest whole pack.

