Remote Data Collection. Participants will complete the two-week study remotely using EMA methods. At the conclusion of Session 1, participants will be trained to record their assigned product use via EMA for data collection. Specifically, participants will respond to 5 scheduled questionnaires daily. These questionnaires are designed to assess product consumption, context of use (e.g., location, social situation), and subjective responses (e.g., withdrawal, product evaluation, message attention - more details on surveys provided below). Participants will be prompted to measure their exhaled-air CO level and product weight twice each day using a personal monitor provided to them. Participants will also retain all spent cigarette butts and unused products throughout the two weeks.

Day 3 Check-in: Research assistants will monitor EMA data to ensure the participant is compliant with study procedures. Participants will send a secure text message (via Twilio) or arrange a phone call to discuss the participant's compliance in the initial days of data collection. Participants that are not responding to prompts will be retrained to ensure they understand procedures and warned that compliance must increase to continue participating in the study.

Session 2 will take place one week later (\pm 2 days) via remote videoconference using an institution-approved software with a password protected meeting (e.g., WebEx, Microsoft Teams, Zoom). The Session 2 videoconference will include the completion of questionnaires on vent awareness, product evaluation, and readiness to quit (similar to Visit 1). Participants will again be asked on message perceptions, but only in relation to their randomly assigned condition.

Session 3 will take place one week later (\pm 2 days) via remote videoconference. The same questionnaires from Session 2 will be administered again. Laboratory staff will guide participants to place all materials (retained filter butts, unused products, unsigned payment receipts) in the provided shipping box. Arrangements will be made for the participant to return materials or for research staff to pick up materials. Participants will be paid for Visit 3 upon verification of returned study materials.

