22 STATISTICAL PLAN

22.1 Data Analysis Plan

The analysis of EMA data will be analyzed using a linear mixed model with fixed effects for vent message (product design, color/name), as well as sex and other tobacco product strata (cigarettes only or dual use). The effect of packaging will be tested using a Bonferroni-corrected type-I error rate of 0.008 (0.05/6) to account for all possible pairwise comparisons of packaging types. Data from the field-study (e.g., change in product responses, risk, TNE, aldehyde-DNA adducts) will be analyzed using linear regression with terms in the model for vent message (no message, neutral, compensation, blocking), sex, and other tobacco product use.. Categorical outcomes for the field-study will be analyzed using logistic regression. As exploratory approaches, we will use time-varying effects models (TVEMs) to explore the effect of message condition on smoking behavior (product compliance), craving, risk perception, and quit intention in the EMA data.[191, 192] TVEMs have been used previously to examine treatment effects on craving [193] and relapse.[194] TVEMs will provide daily effect sizes, thereby allowing us to examine whether treatment effects (and relationships with other predictors) change over time (i.e., early vs. later in product switching). Responses at Visit 1 can be treated as time invariant predictors and mCEQ from EMA can be treated as time-varying predictor (and/or outcome) of product use.

Roswell Park Protocol Number: I 757820

We will enroll a total sample size of 300 subjects and assume a 20% drop-out rate with uniform drop-out from Visit 1 to Visit 3. This will result in a sample size of 300 subjects for Visit 1, 270 subjects for the first week of the field study, and 240 subjects for the end of field study. Our sample size was determined to have adequate power for the field study, For the field study, we hypothesize a 25% difference between conditions, corresponding to a 3.9 CPD difference. Assuming a standard deviation of 7.6,[195] a sample size of 240 subjects will provide 95% power to detect a significant difference between ventilation conditions at the 0.05 level and 80% power to detect a significant difference between packaging conditions with a Bonferroni-corrected type-I error rate of 0.008.

mCEQ is scored using an established algorithm.⁹⁶ This results in 3 subscales (Psychological Reward, Relief, Reward) and 2 single items (Aversion, Respiratory sensation). Scores range from 1-7.

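### Participants withdrawn for failing the diary rule are dismissed, so their remaining Session 2 and 3 questionnaires, including one primary measure with no diary substitute, are never collected

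*Combined protocol and SAP*

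**What the plan says.** Section 12.1 sets two routes to withdrawal without the participant's consent. On the first, three consecutive days below the compliance threshold bring a warning and retraining, and then: "If the participant continues to be noncompliant for 3 additional days, they will be withdrawn from the study". The second is immediate: "Failure to respond to any study prompts (0% compliance) for three consecutive days will result in withdrawal".

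The heading of Section 12.2 allows for partial withdrawal with data collection continuing, but the text beneath it offers none: participants are paid only for the sessions they completed and "then will be dismissed from the study". Appendix D likewise tells participants that they will be discontinued if compliance does not improve.

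Allocation comes earlier. Section 11.3 places it directly after consent and before Session 1: "The participant will then be randomized to 1 of 4 message conditions". Session 2, a week after Session 1 (±2 days), includes "completion of questionnaires on vent awareness, product evaluation, and readiness to quit". Session 3 repeats those questionnaires a week later.

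On attrition, Section 22.1 says only that the investigators "assume a 20% drop-out rate with uniform drop-out from Visit 1 to Visit 3". It analyses the field-study outcomes collected outside EMA by linear regression. It names no analysis set, no way of handling missing session data and no sensitivity analysis.

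**The concern.** The rule links two data streams that need not be linked. A participant who stops answering five prompts a day may still be willing to join a half-hour videoconference, but the protocol ends both together. The study thereby creates missing outcomes of its own, in addition to those from people who leave by choice.

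These losses occur after randomisation, among the least engaged participants. There is also a specific way in which they could depend on arm. The EMA questions in Appendix C ask whether the participant noticed, read or avoided the warning label, and whether it changed how they smoked. Packs in the no-message arm are unaltered (Section 11.2), so the same questions have a different meaning there. The hypothesis in Section 1.2 is that messages lower satisfaction and raise intention to stop. Willingness to keep answering could therefore be related to both the arm and the outcome. If it is, a comparison of those who remain is no longer the randomised comparison, and a smaller planned N does not correct for that.

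**Working it through.** **1. The plan's attrition figure.** 300 × (1 − 0.20) = 240 at the end of the field study, and 300 × (1 − 0.10) = 270 at the uniform midpoint. Both match Section 22.1. The allowance is for number only. It is not split by arm or by reason, and none of it is attributed to the diary rule.

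**2. When withdrawal can occur.** The zero-response route can end participation at about day 3. The warning route needs 3 + 3 days, so about day 6. Session 2 falls between days 5 and 9 (7 ± 2). A withdrawal at day 3 or 4 therefore removes both later sessions. One at day 6 removes both if Session 2 has not yet been held, and otherwise removes Session 3 only.

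**3. What is lost** (schedule in Section 5.1 against the endpoints in Section 3):

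| Measure | Endpoint | Where collected | After dismissal |
|---|---|---|---|
| Contemplation ladder | Primary 1 | Video sessions only | Remaining sessions lost, no EMA substitute |
| Product-evaluation scales | Primary 1 | Video sessions, select items by EMA | Only EMA items and sessions before withdrawal remain |
| Withdrawal, craving and mood scales | Primary 1 | EMA only, select items | Remaining days lost; session follow-up would not recover them |
| Vent awareness | Secondary | Video sessions only | Remaining sessions lost, no EMA substitute |

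**4. Bias in a comparison of completers.** Let l be the proportion lost in an arm and D the mean of those lost minus the mean of those retained. The full-arm mean equals the retained mean + l × D, so the retained mean is off by l × D. Between two arms the error has size |l₁D₁ − l₀D₀|. With the same D in both arms it is |l₁ − l₀| × |D|.

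The documents give neither l by arm nor D. Every input below is an assumption:

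| Loss in the two arms | D | Bias |
|---|---|---|
| 20% v 20% | same in both arms | 0 |
| 5% v 10% | 0.5 SD | 0.05 × 0.5 = 0.025 SD |
| 15% v 25% | 1 SD | 0.10 × 1 = 0.10 SD |
| 10% v 30% | 1 SD | 0.20 × 1 = 0.20 SD |

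Equal loss alone is not enough to remove bias. If 20% are lost in both arms but only one arm's lost participants differ, by 0.5 to 1 SD, the bias is 0.20 × 0.5 = 0.10 SD to 0.20 × 1 = 0.20 SD.

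**5. The threshold decides how many are withdrawn.** Section 12.1 says 80% but glosses it as more than 4 of 5 prompts, which taken literally is 5 of 5 (4/5 is already 80%). Section 11.4 defines compliance for payment as at least 4 of 5. Appendix D tells participants that payment needs all 5. Suppose each prompt is answered independently with probability 0.90 (an assumption). Then:

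- P(all 5) = 0.90⁵ = 0.590, so 41% of days fail under 5 of 5.
- P(at least 4) = 0.590 + 5 × 0.10 × 0.90⁴ = 0.590 + 0.328 = 0.919, so 8% of days fail under at least 4 of 5.

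Real non-response clusters within people, so these figures show only that the readings differ greatly. They do not forecast withdrawals.

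**The case against.** The strongest reply is that the problem may be small. Section 11.4 cites over 90% compliance in studies with similar methods. The protocol has a Day 3 check-in with retraining, a warning step, a discussion of compliance at Sessions 2 and 3, and up to $10 per compliant day. No withdrawal rate by arm is given, so dependence on arm is a plausible inference and not something the documents show. Many withdrawals by the warning route could fall after Session 2 and cost only Session 3. Someone who has answered nothing for three days may not attend a videoconference either. All of this stands, and it is why the size is left open and the range includes zero.

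A reader might also infer several stronger points that the documents do not support:

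- **That the rule breaks the randomised comparison.** It can do so. With equal loss and equal differences it does not.
- **That all primary outcomes from Sessions 2 and 3 disappear.** Some product-evaluation items are also in the diary, vent awareness is secondary, and the withdrawal scales are collected only by EMA.
- **That collected data are thrown away.** No section says so. The loss is of data not yet collected. The EMA mixed model can use diary entries made before withdrawal, if data are missing at random.
- **That keeping these participants would raise power from the planned 60 per arm towards 75.** The planning effect (3.9 with SD 7.6) is for cigarettes per day, the documents give no effect size for the session questionnaires, and the change proposed here stops the prompts that record daily smoking. Nor is the 20% allowance all due to the diary rule. No gain in power is claimed.

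**Conclusion.** The point holds as an avoidable weakness in design. As written, Section 12.2 stops collection of session questionnaires that do not depend on the diary. One of them, the contemplation ladder, is part of Primary 1 and has no other source. The loss follows randomisation, could be related to arm, and is not addressed anywhere in Section 22.1.

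The size cannot be determined from the documents. The illustrative range is 0 to 0.20 SD. It rests wholly on assumed loss rates and assumed differences between lost and retained participants, and the direction could be towards or away from the null. If compliance is as high as the cited studies suggest and the more lenient threshold applies, the effect may be slight. The case for acting is that the change is cheap, not that serious bias has been shown.

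**What to change.** Amend Section 12.2 so that failing the EMA rule ends EMA prompts and EMA payments only. Unless consent is withdrawn, the participant is still invited to Sessions 2 and 3 and still returns butts and unused product.

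In Section 22.1:

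- State that all randomised participants are analysed in their assigned arm, using all data collected.
- Report withdrawals by arm and by reason.
- Pre-specify a sensitivity analysis for session outcomes still missing, allowing those lost to differ from those retained and to differ by arm.

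Reconcile the compliance threshold across Sections 11.4 and 12.1 and Appendix D, so that the same rule is applied at all three sites and told to participants.

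The cost is a short amendment, a little staff time, and up to $50 per retained session at the rate in Section 8.4, so at most 2 × $50 = $100 for a participant kept for both. The documents give rates but no budget, so whether this is already funded is not known. The drawback is that retained participants will have sparse diaries and few pack photographs, so their use of the assigned packs will be less well verified. Their results should be read with that in mind.
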